### 5.6.7 Actigraphy (Inactivity) Evaluation

Actigraphy is a non-invasive method of monitoring a person's rest and activity cycles. The movements the actigraphy sensor undergoes are continually recorded.

Actigraphy measurements will be collected for 3 days prior to visit VR and for 3 days at the end of each treatment period. Charged actigraphy devices will be handed out to subjects at visits VS1, VR, V1C, and V2C, and actigraphy data will be collected during visits VR, V1B, V2B, and V3B/EDV.

Objective activity measures will be estimated from the raw activity data by a research team from [REDACTED] and provided to [REDACTED] for efficacy analysis. A description of this process and each evaluated objective activity measure is provided in the AX3 Analysis Plan, attached as an appendix to this SAP (see Section 9).

The following objective activity measures will be estimated for each day prior to the collection visit:

- Night Time Immobility Duration (minutes) (**NTID**)
- Night Time Mobility Periods (**NTMP**)
- Night Time Mobility Duration (minutes) (**NTMD**)
- Diurnal Immobility Periods (**DIP**)
- Diurnal Immobility Duration (minutes) (**DID**)
- Daily Physical Activity (g) (**DPA**)
- Nightly Physical Activity (g) (**NPA**)
- Daily Jerk (g/s) (**DJ**)

The following activity ratios will be estimated once per collection visit:

- Intradaily Variability (**IV**)
- Interdaily Stability (**IS**)
- Relative Amplitude (**RA**)

The results of each activity measure will be summarised at each visit. The mean value of assessments corresponding to the collection visit will be used for analysis. All values will be listed.

Activity ratios (**IV**, **IS**, **RA**) and physical activity variables (**DPA**, **DJ**) will additionally be analysed using a mixed linear regression model as described in Section 5.6.1.

In the case that a statistically significant ( $p$ -value  $< 0.05$ ) treatment by period interaction is found in the analysis of an objective actigraphy measure, an additional analysis will be performed for that activity measure using only data collected during the first treatment period. The statistical model will be adjusted as described in Section 5.6.1.

Further statistical analyses of actigraphy data are defined outside the scope of this SAP.

The following tables and listing will be presented:

Table 15.3.12.1.1.S Summary of Objective Activity Measures – Full Analysis

Table 15.3.12.1.2.S Summary of Objective Activity Measures – Per Protocol

Table 15.3.12.2.1.T Summary of Objective Activity Measures – Full Analysis

Table 15.3.12.2.2.T Summary of Objective Activity Measures – Per Protocol

Objective activity measures will be summarised using default summary statistics at each visit. The absolute and relative change from baseline will be summarised at each post-baseline visit.

Table 15.3.13.1.1 Analysis of Objective Activity Measures – Full Analysis

Table 15.3.13.1.2 Analysis of Objective Activity Measures – Per Protocol

Table 15.3.13.2.1 Analysis of Objective Activity Measures (First Period) – Full Analysis

Table 15.3.13.2.2 Analysis of Objective Activity Measures (First Period) – Per Protocol

Estimates of each modelled effect will be displayed with standard errors,  $t$ -values and  $p$ -values. Contrast estimates will be displayed for the difference between each pair of treatments.

Listing 16.2.9.4 Objective Activity Measures– Enrolled

## 5.6.8 Subject Diary Data

Over the course of the trial, subjects will fill out paper-based diaries concerning their daily sleep and IMP intake patterns. One screening diary and three treatment diaries will be issued at visit VS1, and visits VR, V1C, and V2C respectively, and collected at visits VR, V1C, V2C, and V3B/EDV. The diaries will be filled in continuously from visit VS1 to V3B/EDV, including the washout periods after treatment periods I and II.

Analysis of drug exposure data collected from subject diaries is discussed in section 5.4.1.

Efficacy-related data collected from patient diaries will be summarized over the respective trial period (baseline, washout 1, washout 2, and treatment 1, 2, or 3) for the purpose of displaying them in summaries. Numeric variables will be standardized to amount per day, and for categorical variables subjects will be included in every category that occurred to them in the given period.

If there are less than 3 non-missing values over the course of a treatment or washout period for a given variable, it will be set to missing for the respective period in summaries. For treatment periods, only the last 3 non-missing values per parameter will be aggregated in summaries order to capture the full effect of the IMP.

All diary data will be listed.

Listing 16.2.9.5 Diary Sleep Data – Enrolled

Listing 16.2.9.6 Diary Exposure Data – Enrolled

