1.4.2. Evaluation of benefit

These subjects have documented excessive daytime sleepiness (EDS) and it is expected that THN102 at one or both doses may significantly improve excessive daytime sleepiness, decreasing episodes of sleepiness and sleep attacks and may even improve night sleep in quantity and quality.

This is a proof-of-concept trial in approximately 60 PD subjects with EDS treated with THN102 at two doses (200 mg/18 mg, 200 mg/2 mg) compared to placebo under a 3-way, double-blind, cross-over trial design. The exposure is thus limited (2 weeks at each dose). This design might contribute to a better understanding of the mode of action of THN102 in the target population, to define the profile for dose response and time response and to assess recovery after washout. If successful, a phase IIb-III trial could be initiated in the future.

In summary, the risk/benefit ratio for this proof-of-concept trial is considered as satisfactory.

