6.1.1. Visit VS1

This screening visit 1 is an on-site visit and will take place between Day -15 and Day -7.

The following procedures will be performed:

- Informed consent
- Hand out subject card
- Demography (incl. height measurement)
- Medical history, prior medication
- Concomitant medication
- Hoehn & Yahr staging
- Check for eligibility
- Adverse event collection
- Safety laboratory (blood [including serology and blood coagulation], urine)
- Pregnancy test (urine), for women of childbearing potential only
- Vital signs (after 5 minutes of supine rest and after 2 minutes in standing position, i.e. 1 set)
- Weight
- 12-lead ECG (10 min supine)
- C-SSRS Screening version
- Physical examination
- ESS
- MoCA
- Issue actigraphy device (fully charged)
- Issue subject diary (screening phase diary)

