#### 4.6 Trial Periods

##### Baseline period

The baseline period will be defined as the period from informed consent signature date to the date of visit VR.

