## 4.7 Baseline and Endpoint Values

### Baseline value

The baseline value for a variable is defined as the last non-missing value collected before or during visit VR.

For diary data, the baseline value will be the value standardised as described in Section 5.6.8 over the baseline period.

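### Night wake-up categories are counted as ever occurring over about 6 to 14 nights at baseline and washout but over only 3 nights on treatment, so on- and off-treatment shares are not comparable

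*SAP*

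**What the plan says.** SAP 5.6.8 has the efficacy-related diary data "summarized over the respective trial period (baseline, washout 1, washout 2, and treatment 1, 2, or 3"). It then treats two kinds of variable differently. Numeric variables are put on a per-day scale. For the other kind, "for categorical variables subjects will be included in every category that occurred to them in the given period". SAP 5.6.8.3 exempts one item from numeric handling: the number of wake-up periods during the night, recorded as fewer than 5, 5 to 10, or more than 10.

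The same section shortens the window for one type of period only: "For treatment periods, only the last 3 non-missing values per parameter will be aggregated in summaries". The stated purpose is to catch the full effect of the drug. Baseline and washout have no such limit. SAP 4.7 confirms this for baseline: "For diary data, the baseline value will be the value standardised as described in Section 5.6.8 over the baseline period". SAP 4.6 sets its length: "The baseline period will be defined as the period from informed consent signature date to the date of visit VR". The diary is issued at VS1, which under Protocol 6.1.1 "will take place between Day -15 and Day -7". Footnote 13 of the flow chart allows washout to extend to 14 days.

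The results go into Tables 15.3.16.1.S and 15.3.16.2.T as frequencies by trial period.

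**The concern.** The chance that a subject shows a category at least once rises with the number of nights examined. A 3-night count is therefore not on the same scale as a 6- to 14-night count, even when sleep has not changed. The per-day scaling means that window length does not shift the mean of the numeric diary variables. The categorical item has no equivalent protection.

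The reading at risk is the one across periods: baseline, then treatment, then washout. SAP 4.8 assigns data from the first two washouts to the preceding treatment, so a table by treatment invites that reading. Protocol 1.4.2 says that the combination "may even improve night sleep in quantity and quality" and that the design might help to assess recovery after washout. In a population that mostly wakes few times a night, the counting rule alone would give fewer bad nights on treatment and more again in washout.

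**Working it through.** The plan states no figure on this point, so there is none to reproduce.

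**Windows**
- Treatment: 3 nights (SAP 5.6.8).
- Baseline: VS1 on Day -15 to Day -7 and VR on Day -1, so 15 − 1 = 14 down to 7 − 1 = 6 nights.
- Washout: V1C on Day 21, −1/+7, after a nominal V1B on Day 14, so 20 − 14 = 6 up to 28 − 14 = 14 days.

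**Assumptions.** The documents give neither the nightly probability p of a category nor the correlation between one subject's nights (ICC). Both are varied below, and no treatment effect is assumed.

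**Independent nights.** Share ever in the category over k nights = 1 − (1 − p)^k. For p = 10% and k = 3, this is 1 − 0.9³ = 27.1%.

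| p | 3 nights | 6 nights | 7 nights | 14 nights |
|---|---|---|---|---|
| 5% | 14.3% | 26.5% | 30.2% | 51.2% |
| 10% | 27.1% | 46.9% | 52.2% | 77.1% |
| 20% | 48.8% | 73.8% | 79.0% | 95.6% |

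**Correlated nights (beta-binomial).** With a = p(1 − ICC)/ICC and b = (1 − p)(1 − ICC)/ICC, the share is 1 − ∏(b + j)/(a + b + j) for j = 0 to k − 1. At p = 10% and ICC 0.5, a = 0.1 and b = 0.9. For 3 nights this gives 1 − (0.9/1)(1.9/2)(2.9/3) = 17.4%.

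| ICC, p = 10% | 3 nights | 7 nights | 14 nights | Gap, 7 / 14 nights against 3 |
|---|---|---|---|---|
| 0 | 27.1% | 52.2% | 77.1% | 25.1 / 50.0 points |
| 0.2 | 22.7% | 36.5% | 48.4% | 13.8 / 25.7 points |
| 0.5 | 17.4% | 23.5% | 28.4% | 6.1 / 11.0 points |
| 0.8 | 12.8% | 14.7% | 16.2% | 1.9 / 3.4 points |

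**All three rows together.** Two assumed nightly mixes, independent nights, 3 against 14 nights:

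| Nightly mix (fewer than 5 / 5 to 10 / more than 10) | Fewer than 5 | 5 to 10 | More than 10 |
|---|---|---|---|
| 70 / 20 / 10% | 97.3% against 100% | 48.8% against 95.6% | 27.1% against 77.1% |
| 10 / 30 / 60% | 27.1% against 77.1% | 65.7% against 99.3% | 93.6% against 100% |

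Every row is lower over 3 nights. In the first mix the fall is mainly in the two unfavourable rows, which looks like improvement. In the second, the largest fall is in the favourable row, which looks like worsening.

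**After correction.** At p = 10% with no effect, the expected proportion of nights is 10% in every period. With 3 nights used everywhere and independent nights, the ever-occurred share is 27.1% in every period.

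**The case against.** The strongest reply is that the comparison the trial is built for is untouched. The objectives set THN102 against placebo, and all three treatments use the same 3-night rule at end of treatment. That stands: the mismatch shifts the placebo column as well and does not create a drug-placebo difference.

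The item is also minor. It is not among the endpoints in SAP 2.2.3. It is descriptive and untested, and SAP 5.6.8.3 asks for no change from baseline on it. Night sleep is also covered by per-day diary variables and by actigraphy, which under SAP 5.6.7 uses 3 days both before VR and at the end of each treatment period. This limits the consequence. It also shows that the plan matches windows elsewhere.

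SAP 4.2 requires baseline and endpoint definitions in table footnotes where applicable. A footnote would disclose the different windows but would not make the shares comparable.

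Two stronger readings are tempting. One is that every treatment, placebo included, is bound to appear to improve night sleep. The documents do not support this, because they give no distribution of night waking and the favourable category shrinks too. The other is that the distortion is 16 to 50 percentage points, the range in the independent-nights table for 7 to 14 nights against 3. Nights within one person are plausibly correlated, and at p = 10% with ICC 0.8 the gap is only about 2 to 3 points.

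**Conclusion.** The rule as written makes the on- and off-treatment shares of this one categorical diary item non-comparable. Whenever a subject's nights vary, each category's expected share is lower on treatment than at baseline or washout with no true change. That follows from the window lengths and needs no assumed probability.

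The size and apparent direction do need assumptions. At p = 10% and 3 against 7 to 14 nights, the gap runs from about 2 to 3 points (ICC 0.8) to 25 to 50 points (independent nights). Whether it resembles benefit or harm depends on how often these subjects usually wake. This is a small point: it concerns one descriptive variable and leaves the end-of-treatment comparisons between A, B and C unbiased. It is still worth correcting, because the stated rule gives a misleading table and the data for a sound one are already collected.

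**What to change.** In SAP 5.6.8, replace the ever-occurred rule by the proportion of recorded nights in each category, calculated per subject and period and summarised as a numeric variable. The 3-night treatment window can stay, since a proportion does not drift with window length. The present minimum of 3 non-missing values covers treatment and washout only, so the same sentence could state a minimum for baseline.

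The cost is one changed sentence, one changed derivation and a revised shell for Tables 15.3.16.1.S and 15.3.16.2.T. No new data are needed.

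The alternative is to keep the categorical rule and use the last 3 recorded nights in every period. This also removes the artefact, but it leaves up to 14 − 3 = 11 baseline or washout nights out of the summary, so the proportion is preferable.

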#### 2.2.3 Secondary Efficacy Endpoints

The secondary efficacy endpoints of this trial are

9. ESS score responder rate, defined as the proportion of subjects with at least 25% ESS improvement from baseline, at the end of each treatment period
10. Absence of residual somnolence, i.e. ESS < 11 at the end of each treatment period
11. Psychomotor Vigilance Test (PVT) variables change from baseline at the end of each treatment period
12. MoCA score change from baseline at the end of each treatment period
13. Actimetry change (inactivity) from baseline at the end of each treatment period
14. Number and duration of diurnal involuntary sleep attacks (subject diaries) change from baseline at the end of each treatment period
15. Episodes of somnolence (subject diaries) change from baseline at the end of each treatment period

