### 4.10 Handling of Missing Data

Data imputation methods will not be used in the analysis of efficacy or safety data. Efficacy data will be assumed to be missing at random (MAR), and likelihood-based estimation methods robust to this form of missingness will be used in efficacy analysis. Other details of handling of missing data, where applicable, are discussed in the relevant sub-sections of Section 5 (*STATISTICAL ANALYSIS: DEFINITIONS, DERIVATIONS, CALCULATIONS AND METHODOLOGY*).

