### 5.6.8.1 Diurnal Involuntary Sleep Attacks

The number and total duration of diurnal involuntary sleep attacks will be recorded in the subject diaries. These data will be summarised as numeric variables as described in section 5.6.8.

The following tables will be presented:

Table 15.3.14.1.S Summary of Diurnal Involuntary Sleep Attacks – Full Analysis

Table 15.3.14.2.T Summary of Diurnal Involuntary Sleep Attacks – Full Analysis

The number and duration of diurnal involuntary sleep attacks will be summarised using default summary statistics for each trial period. The change from baseline will be displayed for each post-baseline period.

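### SAP 5.6.8 has no zero-duration rule for days without a sleep attack; if those days are left blank, the duration summary is per attack day, can report early values as end-of-period values, and drops subjects with 0 to 2 attack days

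*SAP*

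**What the plan says.** Endpoint 14 is defined in SAP 2.2.3 as "Number and duration of diurnal involuntary sleep attacks (subject diaries) change from baseline at the end of each treatment period". SAP 5.6.8.1 treats its two halves as separate numeric diary variables: "The number and total duration of diurnal involuntary sleep attacks will be recorded in the subject diaries". Both are handled by the general rules of SAP 5.6.8:

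- Scale: "Numeric variables will be standardized to amount per day".
- Treatment periods: "only the last 3 non-missing values per parameter will be aggregated in summaries order to capture the full effect of the IMP".
- Treatment and washout periods: "If there are less than 3 non-missing values over the course of a treatment or washout period for a given variable", that variable drops out of the period's summary.

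In washout only the minimum of three applies, and all values present are used. For baseline, SAP 4.7 says: "For diary data, the baseline value will be the value standardised as described in Section 5.6.8 over the baseline period". No minimum number of values is stated there.

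The documents do not say whether a day without an attack is recorded as 0 minutes or left blank, nor that duration is 0 when the number is 0. The results appear only as descriptive statistics on the FAS (Tables 15.3.14.1.S and 15.3.14.2.T). Nap duration is summarised under the same rules (SAP 5.6.8.3).

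**The concern.** The rule counts recorded values, not diary days. For the number of attacks this makes no difference as long as a 0 is written on quiet days. Duration is different: on a day without an attack there is nothing to time, and a blank field is a plausible entry on a paper diary. If that happens, quiet days vanish from the duration variable and three things follow in treatment periods.

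1. The figure labelled as an amount per day is a mean over attack days.
2. The three-value window slides back past the quiet days. A subject with three or more early attack days who then stops is shown at the early value instead of 0.
3. A subject with 0, 1 or 2 attack days in the period is set to missing.

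Number and duration in the same table can then describe different days. Missing values would depend on the outcome, and there would be more of them on whichever treatment reduces attacks more. The window was chosen to show the full effect of treatment; in case 2 it shows the opposite. Endpoint 14 has no model or test, so these tables are its only planned result.

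**Working it through.** The plan gives no sample size, power or expected value for diary data, so there is no figure of its own to reproduce. Its one power statement concerns ESS and has no bearing here.

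**Step 1: the rule applied to constructed diaries.** From the documents: a 14-day treatment period, the last three values, and a minimum of three. Assumed: 20 minutes on each attack day.

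| Attack pattern | Quiet days blank | Quiet days 0 |
|---|---|---|
| Every day | 20 | 20 |
| Every third day | 20 | 20/3 = 6.7 |
| Days 1–7, then none | 20 | 0 |
| Days 1–3, then none | 20 | 0 |
| Days 1–2, then none | missing | 0 |
| None | missing | 0 |

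The last two rows are lost from the summary. The two rows above them are not lost, but report 20 min/day when the end-of-period value is 0.

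**Step 2: size of the overstatement.** If an attack day has probability p, the blank-coded mean exceeds the true daily mean by a factor 1/p: 2 at p = 0.5, 3.3 at 0.3, 5 at 0.2.

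**Step 3: change from baseline.** Assumed: attacks per day are Poisson with mean λ, 15 minutes each, days independent, the same rate for every subject, and λ = 1 at baseline.

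- True daily duration = 15λ.
- Attack-day probability p = 1 − e^(−λ).
- Printed value with blanks = 15λ / (1 − e^(−λ)).
- Chance of being set to missing = (1−p)^14 + 14p(1−p)^13 + 91p²(1−p)^12.

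Baseline: 15/0.632 = 23.7, against a true 15.

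| True reduction | λ | True min/day | Printed min/day | Printed reduction | Set to missing |
|---|---|---|---|---|---|
| 50% | 0.5 | 7.5 | 7.5/0.393 = 19.1 | 1 − 19.1/23.7 ≈ 20% | 0.001 + 0.008 + 0.035 ≈ 4% |
| 75% | 0.25 | 3.75 | 3.75/0.221 ≈ 17.0 | 1 − 17.0/23.7 ≈ 29% (28.6% unrounded) | 0.030 + 0.120 + 0.222 ≈ 37% |
| 90% | 0.1 | 1.5 | 1.5/0.095 ≈ 15.8 | 1 − 15.8/23.7 ≈ 33–34% | 0.247 + 0.363 + 0.248 ≈ 86% |

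Simulation under the same assumptions agrees with the 50% and 75% printed values and with the 37% and 86% missing, to within simulation error.

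**Step 4: washout.** In a seven-day washout the minimum of three alone removes 23% of subjects at p = 0.5, 65% at 0.3 and 85% at 0.2.

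**The case against.** The strongest objection is that the harm depends on a form nobody can see here. The field is a daily total, 0 is a natural entry for it, and diaries are checked at the on-site visits. If 0 is always written, none of the above occurs. This stands, and is why the point is conditional. The SAP is nevertheless silent on which coding to expect, and its rule gives sensible results under only one of them.

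Second, the table would give some warning. The default statistics include n, so lost subjects would show as a smaller n for duration than for number. The number of attacks and the somnolence episodes would still show a benefit, and all diary data are listed. That limits the damage but does not correct the duration figure. A normal-looking n would also not reveal subjects reported at early values.

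Third, the sizes rest on one assumed baseline rate, a fixed 15 minutes and equal rates for all subjects. They illustrate and do not predict. The SAP also speaks of aggregating and standardising, so averaging over the selected values is a reading of its text, though the natural one.

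A reader might infer more than the documents support in three places:

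- That every subject whose attacks stop is set to missing. This holds only with fewer than three attack days in the period.
- That SAP 4.10 forbids the zero, since it says "Data imputation methods will not be used in the analysis of efficacy or safety data". Deriving a duration of 0 from a recorded count of 0 is not imputation, so 4.10 does not stand in the way.
- That the same repair works for night wake-up duration. SAP 5.6.8.3 records the number of wake-ups in categories whose lowest is below five, with no zero category, so nights without waking cannot be identified from it.

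**Conclusion.** The point holds in conditional form. SAP 5.6.8 lacks a zero rule for duration and selects values variable by variable. If duration is blank on quiet days, the treatment-period figure is per attack day, can come from early in the period, and excludes subjects with 0 to 2 attack days. Under the stated Poisson assumptions, a true halving prints as about a 20% reduction, and a true 75% reduction as about 29% with about 37% of subjects missing. If 0 is always entered, the bias is nil.

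The reach is limited to the descriptive summaries of endpoint 14 and to nap duration. A reader might take it as a threat to the trial's efficacy conclusion, but the key ESS analysis and the safety objective do not use these values.

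**What to change.** Add to SAP 5.6.8:

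> On a diary day with the number of sleep attacks (or naps) recorded as 0, total duration is set to 0 (a derivation, not an imputation). In treatment periods, number and duration are both taken from the same last 3 diary days with a recorded number.

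A day with a recorded number above 0 and no duration remains missing for duration. The rule relies on the number being entered as 0 on quiet days; the diary sleep listing (16.2.9.5) would show whether it was.

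The cost is two SAP sentences and a short derivation, with no new data. If zeros are already entered on every day, the printed values do not change. No zero rule should be added for night wake-up duration on the fields listed.

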1. There is no Day 0 (D0), i.e. the day after D-1 is D1. First IMP intake will be on Day 1. (On the day after V1C for treatment period II, on the day after V2C for treatment period III).
2. Safety laboratory will include haematology, biochemistry and urinalysis. At VS1 also serology and blood coagulation.
3. Urine pregnancy tests will be done in women of childbearing potential only. They may be performed more frequently to meet country-specific requirements.
4. Vital signs: Systolic and diastolic blood pressure as well as heart rate will be measured twice: after 5 minutes of supine rest and after 2 minutes in standing position (one set). At VR, V1C and V2C three sets of supine and standing vital signs will be measured 15-20 min apart.
5. Weight will be measured in street clothes without shoes.
6. At VS1 the C-SSRS Screening version will be completed. At other visits, the C-SSRS Since Last Visit version will be completed.
7. PVT will be done at 10:00 h, 12:00 h, 14:00 h and 16:00 h (± 0:15 h each). If this PVT assessment schedule is too burdensome for the subject, it may be individually adapted to at least 3 assessments, with a time window of not less than 1 h between two PVT assessments. Once chosen, the timeframe should remain constant during the trial for each subject.

8. The subject diary will be used continuously (i.e. also during washout periods) to record get-up time, total time (hours) slept last night, wake-up periods during night sleep, time of drug intake and number of capsules taken (except screening phase diary issued at VS1), somnolence episodes, diurnal involuntary sleep attacks, voluntary naps, number of caffeinated drinks and going-to-bed time.
9. Visits V1A and V1B should be scheduled so that 3 days of actigraphy data can be collected. (The same for VS2 and VR, V2A and V2B, as well as V3A and V3B.) Actigraphy will be assessed using an actigraphy wrist band.
10. MoCA should be performed in the morning.
11. In case of early discontinuation, the same procedures as required for V3B will be performed.
12. One PK blood sample will be taken when the subject arrives on the site. The times of blood withdrawal must be recorded.
13. Starting from Day 21, the visit day numbers are theoretical, as the washout period is flexible and can be extended to up to 14 days. The 2-week duration of the treatment period is fixed.

TABLE OF CONTENTS

TRIAL SYNOPSIS	6
TRIAL FLOW CHART	12
LIST OF TABLES	17
LIST OF ABBREVIATIONS	18
1. INTRODUCTION.....	20

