1.3. Rationale for Trial Design and Dose Selection

1.3.1. Trial design

This proof-of-concept, phase IIa trial with THN102 should collect a sufficient body of information to assess the safety and efficacy profile of THN102 versus placebo in Parkinson's disease subjects suffering from excessive daytime sleepiness. The sample size required for a crossover design is approximately one third of the size required in a parallel trial. To use a cross-over option is thus a viable alternative design, with a sample size of about 60 subjects in this condition. In addition, a direct comparison between THN102 doses can be performed in the same subject. The selected trial design for this pilot proof-of-concept phase IIa trial is consequently a randomised, placebo-controlled, 3-way cross-over trial design comparing two dose levels of THN102 to placebo and followed by a washout period of 1-2 weeks. It was perceived as essential to take advantage of the cross-over design for exploring two doses of THN102 and comparing their impact on safety, ESS and other efficacy endpoints. The treatment duration of 2 weeks per period appears sufficient to observe therapeutic activity as the steady state will be reached after about 3 days of drug intake. Each treatment period is followed by a one-week washout period, which can be extended up to two weeks. In addition to the key efficacy endpoint, ESS, other efficacy endpoints have been selected, such as cognitive assessments including PVT and MoCA before and after each treatment period.

A difference of 25% in ESS is considered clinically relevant. [26] Therefore responder rates will be analysed, with responders being defined as subjects with at least 25% improvement from baseline.

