5.1.3. Timing of IMP doses and administration

IMP will be administered only to subjects included in this trial, following the procedures set out in the trial protocol.

IMP (2 capsules modafinil or placebo plus 2 capsules flecainide or placebo; 4 capsules in total) will be administered in the morning. IMP will be swallowed before meal with 150 mL tap water at 8:00 h (\pm 1 h).

For subjects aged above 65 years:

On the first, second and third day of each treatment period, 1 modafinil and 1 flecainide capsule will be taken. From the fourth to the last day of each treatment period, the regimen will be as described above.

The time of IMP intake will be recorded in the subject diary daily.

Dose adjustments will not be permitted.

In each treatment period, first IMP intake will take place on the day after IMP dispensation, i.e. on the day after visit VR, V1C or V2C, respectively.

In each treatment period, last IMP intake will take place on the day of visit V1B, V2B or V3B, respectively.

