##### Treatment periods

The periods from the day after visits VR, V1C, and V2C, to the dates of visits V1B, V2B, and V3B respectively, will be defined as the three treatment periods of this trial.

Data collected at visits V1B, V2B, and V3B will be considered as end-of-treatment values for their respective treatment periods.

If an early discontinuation visit (EDV) occurs after 7 or more IMP intakes, and not more than 3 days after the last IMP intake, the data collected at the EDV will be assigned to the end of the ongoing treatment period for statistical analyses.

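### The SAP's diary rule has no calendar window, so sparse or early-stopped diaries can put first-week values into the end-of-treatment tables for sleep attacks and somnolence episodes

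*SAP*

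**What the plan says.** SAP 5.6.8 sets two conditions for diary data in a treatment period. A variable is set to missing "If there are less than 3 non-missing values over the course of a treatment or washout period for a given variable". Otherwise "only the last 3 non-missing values per parameter will be aggregated in summaries", and the reason given is in "order to capture the full effect of the IMP".

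SAP 4.6 defines the treatment periods as "The periods from the day after visits VR, V1C, and V2C, to the dates of visits V1B, V2B, and V3B respectively", so period day 1 is eligible. SAP 4.7 makes the 5.6.8 value the diary endpoint value. SAP 2.2.3 defines both diary endpoints at the end of treatment; endpoint 15 reads "Episodes of somnolence (subject diaries) change from baseline at the end of each treatment period", and endpoint 14 (sleep attacks) has the same timing.

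Two protocol statements bear on the early days. Protocol 1.3.1 says "the steady state will be reached after about 3 days of drug intake". For subjects above 65, Protocol 5.1.3 says "On the first, second and third day of each treatment period, 1 modafinil and 1 flecainide capsule will be taken", which is half the usual number of capsules.

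**The concern.** The rule orders entries by recency but does not limit how old the latest three may be. If a subject stops filling in a diary item early, or fills it in rarely, the three values can come from the first week. The table would still label them as end of treatment. Entries from days 1 to 3 precede the protocol's own steady state at any age and are at reduced dose for subjects over 65.

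The evaluability rules in SAP 5.6 do not close the gap. They require at least 7 days of IMP and a last intake no more than 3 days before the visit, but they say nothing about the dates of diary entries. A period can satisfy both and still take its diary values from its first days.

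For endpoints 14 and 15 the descriptive tables are the only planned result, so no model or per-protocol table would show the mistiming.

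**Working it through.** The plan gives no figure to reproduce here: it states no diary missingness rate. The check applies the rule as written and shows a range.

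**Inputs**
- Period length: 14 days. The trial flow chart says "The 2-week duration of the treatment period is fixed", with the end-of-treatment visit on Day 14 ± 2, so 12 to 16 days.
- Days 1 to 3: reduced dose for subjects over 65 (Protocol 5.1.3) and before steady state (Protocol 1.3.1).
- Daily probability that an entry is missing, m: assumed, independent between days. Write o = 1 − m.

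**Entries stop after day k**
- k = 3: days 1–3 are used, 3 of 3 from days 1–3.
- k = 4: days 2–4 are used, 2 of 3.
- k = 5: days 3–5 are used, 1 of 3.
- k = 6 or 7: none from days 1–3, but all three values are still from the first week.

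**Entries missing at random days, 14-day period**

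A. At least one first-week entry is used. This needs at most 2 entries on days 8–14 and at least 3 in total:
Σ (j = 0 to 2) C(7,j) o^j m^(7−j) × P(Bin(7,o) ≥ 3 − j).
At m = 0.5: (1×99 + 7×120 + 21×127)/16384 = 3606/16384 = 22.0%.

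B. At least one entry from days 1–3 is used. This needs at most 2 of the 11 entries on days 4–14 and at least 3 in total:
Σ (j = 0 to 2) C(11,j) o^j m^(11−j) × P(Bin(3,o) ≥ 3 − j).
At m = 0.5: (1×1 + 11×4 + 55×7)/16384 = 430/16384 = 2.6%.

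C. Period set to missing under a 7-day window: P(Bin(7,o) ≤ 2).
At m = 0.5: (1 + 7 + 21)/128 = 29/128 = 22.7%.

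| Daily missingness m (assumed) | A: first-week entry used | B: day 1–3 entry used | C: missing under 7-day window |
|---|---|---|---|
| 0.1 | 0.02% | <0.001% | 0.02% |
| 0.3 | 2.9% | 0.06% | 2.9% |
| 0.5 | 22.0% | 2.6% | 22.7% |
| 0.7 | 48.6% | 15.2% | 64.7% |

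The present rule already loses (1 + 14 + 91)/16384 = 106/16384 = 0.65% of periods at m = 0.5. The extra loss from the window is 3712/16384 − 106/16384 = 3606/16384, which equals A. The window therefore removes exactly the periods that now draw on the first week.

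For 12- to 16-day periods, B runs from 7.1% down to 0.9% at m = 0.5. All three values coming from days 1–3 has a probability below 0.11% in every case computed.

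**Does a window work?** For a visit on day 12, 14 or 16, a 7-day window covers days 6–12, 8–14 or 10–16. None reaches day 3. A day-4 floor adds something only for an early discontinuation visit, which SAP 4.6 can assign to the end of treatment after 7 intakes. On day 7 the window would be days 1–7.

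**The case against.** The best defence is that the reduced-dose case is remote. It needs at most 2 of 11 later entries and applies only to subjects over 65. Diaries are inspected at visits (Protocol 6.4.5), and diary compliance below 80% goes to case-by-case review (SAP 5.1.2, PD#25). A subject over 65 with capsule entries for days 1–3 only would show (3×2)/(3×2 + 11×4) = 6/50 = 12%. This largely stands. However, the rule works per parameter, so a sleep-attack item can be blank while the capsule count is complete. A flag also does not by itself remove the value from the Full Analysis Set tables.

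A second defence is that a window discards 23% of periods at 50% missingness to prevent 2.6% contamination. That counts only days 1–3. Against first-week entries the trade is one for one, although days 4–7 are at full dose and the harm there is milder. If diary-keeping depends on sleepiness, a window also turns mistimed values into possibly informative missing ones. That is a real cost, and it is why the losses should be reported.

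A reader might go further and infer that off-drug days contaminate the tables when a subject stops IMP but keeps the diary. The documents do not support that as a general fault. SAP 5.6 makes a period evaluable only with at least 7 days of IMP, and it deliberately tolerates up to 3 missed intakes before the visit. Restricting entries to days with intake would select on behaviour after randomisation, against the as-randomised policy (SAP 4.8; Protocol 8.3 and 8.3.1).

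**Conclusion.** The point holds in a limited form. The rule as worded does not secure its stated aim: an evaluable period with sparse or early-stopped diary entries can report first-week values, some before steady state, as end of treatment for endpoints 14 and 15. It affects descriptive Full Analysis Set tables only, and the ESS analysis is untouched. This is a cheap improvement.

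How often it happens cannot be known from the documents. With light missingness it is rare. The percentages rest on assumed, independent daily missingness; subjects who stop writing altogether would make it more frequent.

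Two stronger readings should be resisted. A reader might infer that the active–placebo difference shrinks by the share of affected periods. That needs a share the documents do not give and no drug effect at all on early days, which they do not state. A reader might also see a contradiction with the SAP's revision history, which describes the last 3 days before the visit. A change log is not the operative text, so this is not counted as an error.

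**What to change.** Amend SAP 5.6.8 so that the last 3 non-missing values must come from a fixed calendar window ending at the end-of-treatment visit, or at an early discontinuation visit that qualifies under SAP 4.6. One workable choice is the last 7 days of the treatment period and none before day 4. If fewer than 3 values fall in the window, set the period value to missing. Report the number of periods lost for each treatment. Apply the SAP 5.6 evaluability rules as already written, and do not add a condition on IMP intake for individual diary days.

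This matches the endpoint definition and sits closer to the actigraphy collection in SAP 5.6.7, which uses 3 days at the end of each treatment period. It is an analysis window and changes no dosing rule.

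The cost is one sentence and more missing diary summaries: about 3% of periods at 30% daily missingness and 23% at 50%, both assumed rates.
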